#### 4.2 Survival Follow-up

Survival Follow-up 				
	Every 3 months until disease progression or subsequent treatment	At disease progression or initiation of subsequent therapy	Every 6 months after disease progression or initiation of subsequent therapy	At death
Event Monitoring	X	X	X	X

1. If a patient is still alive 5 years after registration, no further follow-up is required.

**5.0 Stratification Factors OR Grouping Factor:**

None.

**6.0 Registration/Randomization Procedures****6.1 Registering a patient**

To register a patient, access the Mayo Clinic Cancer Center (MCCC) web page and enter the registration/randomization application. The registration/randomization application is available 24 hours a day, 7 days a week. Back up and/or system support contact information is available on the website. If unable to access the website, call the MCCC Registration Office at [contact] between the hours of 8 a.m. and 5:00 p.m. Central Time (Monday through Friday).

The instructions for the registration/randomization application are available on the MCCC web page (<http://ccswww/training/index.html>) and detail the process for completing and confirming patient registration. Prior to initiation of protocol treatment, this process must be completed in its entirety and an MCCC subject ID number must be available as noted in the instructions. It is the responsibility of the individual and institution registering the patient to confirm the process has been successfully completed prior to release of the study agent. Patient registration via the registration/randomization application can be confirmed in any of the following ways:

- Contact the MCCC Registration Office [contact]. If the patient was fully registered, the MCCC Registration Office staff can access the information from the centralized database and confirm the registration.
- Refer to "Instructions for Remote Registration" in section "Finding/Displaying Information about A Registered Subject."

**6.2 Verification of information**

Prior to accepting the registration, the registration/randomization application will verify the following:

- IRB approval at the registering institution
- Patient registration eligibility
- Existence of a signed consent form
- Existence of a signed authorization for use and disclosure of protected health information.

**6.3 Documentation of IRB approval**

Documentation of IRB approval must be on file in the Registration Office before an investigator may register any patients.

In addition to submitting initial IRB approval documents, ongoing IRB approval documentation must be on file (no less than annually) at the Registration Office ([contact]). If the necessary documentation is not submitted in advance of attempting patient registration, the registration will not be accepted and the patient may not be enrolled in the protocol until the situation is resolved.

When the study has been permanently closed to patient enrollment, submission of annual IRB approvals to the Registration Office is no longer necessary.

**6.4** Correlative Research

6.41 A mandatory correlative research component is part of this study, the patient will be automatically registered onto this component (see Sections 3.18, 14.1).

**6.5** Treatment on protocol

Treatment on this protocol must commence at Mayo Clinic Rochester or Mayo Clinic Florida under the supervision of a medical oncologist/hematologist.

**6.6** Treatment start

Treatment cannot begin prior to registration and must begin  $\leq$  28 days after registration.

**6.7** Pretreatment

Pretreatment tests/procedures (see [Section 4.0](#)) must be completed within the guidelines specified on the test schedule.

**6.8** Baseline symptoms

All required baseline symptoms (see [Section 10.6](#)) must be documented and graded.

**6.9a** Study drug

Study drug is available on site.

**6.9b** Blood draw kits

Blood draw kit is available on site.

**6.9c** Study Conduct

The clinical trial will be conducted in compliance with regulations (21 CFR 312, 50, and 56), guidelines for Good Clinical Practice (ICH Guidance E6), and in accordance with general ethical principles outlined in the Declaration of Helsinki; informed consent will be obtained from all participating patients; the protocol and any amendments will be subject to approval by the designated IRB prior to implementation, in accordance with 21 CFR 56.103(a); and subject records will be stored in a secure location and subject confidentiality will be maintained. The investigator will be thoroughly familiar with the appropriate use of the study drug as described in the protocol and Investigator's Brochure. Essential clinical documents will be maintained to demonstrate the validity of the study and the integrity of the data collected. Master files should be established at the beginning of the study, maintained for the duration of the study and retained according to the appropriate regulations.

## 7.0 Protocol Treatment

Both the study drugs are to be self-administered by the patients. Ibrutinib is administered daily as 3 tablets and ixazomib is to be taken as per the schedule below. Ixazomib may be administered by the patient within  $\pm 1$  day of the scheduled dose.

### 7.1 Treatment Schedule

Table 7.1a

Agent	Dose	Route	Day	Cycles*
Ixazomib	4 mg	PO	1, 8, 15	Cycle 1-24
Ibrutinib	420 mg	PO	1-28	Cycle 1-24

\*All Cycles = 28 days each (except at treatment completion where cycle length will be the number of treatment days in that cycle + 28 days)

Any dose adjustments will be made as per guidelines in section 8.

Use actual weight or estimated dry weight if fluid retention

Treatment Schedule (in case of dose de-escalation required after safety analysis of first 6 patients as per Section 16.215)

Table 7.1b

Agent	Dose	Route	Day	Cycles*
Ixazomib	3 mg	PO	1, 8, 15	Cycle 1-24
Ibrutinib	420 mg	PO	1-28	Cycle 1-24

\*All Cycles = 28 days each (except at treatment completion where cycle length will be the number of treatment days in that cycle + 28 days)

Any dose adjustments will be made as per guidelines in section 8.

Use actual weight or estimated dry weight if fluid retention

### 7.2 Treatment by local medical doctor (LMD)

Treatment by a local medical doctor (LMD) is not allowed.

### 7.3 Return to treating institution

For this protocol, the patient must return to the consenting institution for evaluation and drug administration at least every 28 days during treatment for the first 4 cycles. After cycle 4, patients may elect to return every other cycle per treating MD's discretion as long as there are no active ongoing toxicities that have not returned to baseline. Clinical evaluation and blood tests can be obtained per test schedule and mailed/faxed to the consenting institution and patient can return at least every other cycle for follow up to the consenting institution. The cycle length will remain at 28 days and data collection forms will be due at the end of each cycle. Adverse events and adherence to study treatment will be collected at the end of each cycle by telephone for cycles where the patient does not return to the clinic. The patient should retain the pill diaries and medication bottles (even if unopened or empty) along with any unused pills for each cycle and bring them to their next visit so that dosing can be recorded on the evaluation/treatment forms for each cycle.

## 8.0 Dosage Modification Based on Adverse Events

A dose of ixazomib and ibrutinib (as per attribution by the treating physician) is held if a patient experiences any of the following considered at least possibly related to ixazomib and/or ibrutinib at the beginning of a new cycle of treatment:

- ANC <1,000/mm^3 (grade 2)
- Platelet <75,000/mm^3 (grade 1)
- Any other nonhematologic toxicity (except for alopecia or fatigue)  $\geq$  grade 3 with the

following considerations:

- Grade 3 nausea, vomiting or diarrhea will be considered significant if they occur despite appropriate maximal anti-emetic and/or antidiarrheal therapy.
- Grade 3 hyperglycemia will be considered significant if the patient is symptomatic or glucose level is >300 mg/ml despite appropriate administration of insulin and/or oral antidiabetic agents.

→ **ALERT:** **ADR reporting may be required for some adverse events (See Section 10.0)** ←

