#### 4.0 Test Schedule

##### 4.1 Test schedule for Waldenström Macroglobulinemia

Tests and procedures	≤ 28 days prior to registration	≤ 14 days prior to registration	Cycle 1				Cycles 2-24 (During course of treatment) 	(End of treatment)	Clinical Follow-up
			Day 1	Day 8	Day 15	Day 22	Day 1	4 weeks after last study drug intake	Q 3 months X 2 years
Window			±3 days				±7 days		±7 days
Informed Consent	X								
Complete medical history 		X	X						
Physical exam, vital signs Wt, PS		X	X				X	X	X
Pregnancy test 		X							
Hematology group CBC w/diff		X	X	X	X	X	X	X	X
Chemistry group Sodium Chloride Potassium Magnesium Phosphate Uric acid BUN Glucose ALT/AST Alkaline phosphatase Total protein Total Bilirubin Direct Bilirubin Albumin Serum creatinine Creatinine clearance calcium		X	X	X	X	X	X	X	X

Tests and procedures	≤ 28 days prior to registration	≤ 14 days prior to registration	Cycle 1				Cycles 2-24 (During course of treatment) 	(End of treatment)	Clinical Follow-up
			Day 1	Day 8	Day 15	Day 22	Day 1	4 weeks after last study drug intake	Q 3 months X 2 years
Bone marrow aspirate and biopsy 	X						X	X	X
Electrophoresis of serum and urine (SPEP/UPEP)		X 					X 	X 	X 
Affected immunoglobulins 		X					X	X	X
Immunofixation serum and urine (IF)		X					X	X	X
Immunoglobulin free light chains (FLC)		X					X	X	X
Serum beta-2-microglobulin, LDH, serum viscosity		X					X	X	X
Tumor measurement 		X					X	X	X
EKG or ECHO or MUGA 		X					X	X	X
Adverse event monitoring		X	X	X	X	X	X	X	X
Patient Medication Diary (Appendix II) 			X				X	X	
Research Bone Marrow Aspirate Sample R (see Section 14.0)		X 					X 	X 	
Mandatory Research blood specimens (see Section 14.0) 8,R		X 					X	X	

Cycle = 28 days (except at treatment completion where cycle length will be the number of treatment days in that cycle + 28 days)

1. Does not need to be repeated on cycle 1, day 1 if completed within 5 days. A complete physical exam, including height (screening only) and weight, neurologic assessment and assessment for lymphadenopathy/organomegaly will be conducted at screening, day one of each cycle, end

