6. To be performed at screening and as clinically indicated throughout the study. Check EKG at any time if the patient's vital signs suggest an issue or if the patient has complaints that could be related to atrial fibrillation as per the physician's assessment.
7. The diary must begin the day the patient starts taking the medication and must be completed per protocol and returned to the treating institution OR compliance must be documented in the medical record by any member of the care team.
8. Blood specimens will be collected and submitted as specified in Section 14.0. Kits are required.
9. UPEP testing required at baseline only. Subsequent testing will be as needed per physician discretion.
10. Collected at registration but prior to treatment
11. After Cycle 1, Additional samples to be drawn if a bone marrow is done for confirmation of response or as otherwise clinically indicated.
12. Patient return visit requirements: Day 1 of cycles 1, 2, 3 and 4. After cycle 4, the patient may be allowed to come every other cycle (to coincide with cycle 6, 8, 10, 12, 14, 16, 18, 20, 22, 24) if considered appropriate by the treating physician. (See section 7.3)

R Research funded (see Section 19.0)

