#### Additional Adverse Events:

Grade  $\geq 3$  non-hematological toxicity (other than peripheral neuropathy) considered at least probably related to ixazomib:

- Omit ixazomib until resolution to Grade  $\leq$  1 or baseline, then restart at the same dose.
- If not recovered to  $\leq$  Grade 1 or baseline despite adequate supportive care within 4 weeks, then the patient may continue on single-agent ibrutinib till the completion of treatment and then proceed to survival follow-up.
- For reoccurrence of  $\geq 3$  non-hematological toxicity (other than peripheral neuropathy) omit ixazomib until resolution to Grade  $\leq$  1 or baseline, then restart at one lower dose level.
- **For  $\geq 3$  nausea, vomiting or diarrhea:** Once the ixazomib is omitted and the toxicity recovers to Grade  $\leq$  1 or baseline within 4 weeks of holding ixazomib, it should be restarted at one lower dose level.
- Once ixazomib is reduced for any toxicity, the dose may not be re-escalated. If it is ultimately determined that therapy with ixazomib is no longer safe, the patient may continue on ibrutinib until completion of treatment and then proceed to survival follow.

- If multiple AEs are seen, administer the dose based on the greatest reduction required by any single AE observed. Dose modifications are for AEs attributed to study treatment only. Dose modifications are not required for AEs if they are deemed unlikely or unrelated to study treatment.

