## 8.3 Ibrutinib dose modifications

CTCAE System/Organ/Class (SOC)	ADVERSE EVENT	AGENT	ACTION**
Investigations	Neutrophil count decreased Grade 4	Ibrutinib	If the AE does not return to $\leq$ Grade 2 after reduction of ixazomib to 2.3 mg, then reduce ibrutinib dose as per table 8.1. If no recovery on the 140 mg dose level, then discontinue study therapy and then proceed to survival follow-up.
Investigations	Platelet count decreased Grade 4		If the AE does not return to $\leq$ Grade 1 after reduction of ixazomib to 2.3 mg, then reduce ibrutinib dose as per table 8.1. If no recovery on the 140 mg dose level, then discontinue study therapy and then proceed to survival follow-up.

\*\* Use the following to describe actions in the Action column:

- **Omit** = The current dose(s) for the specified drug(s) during a cycle is skipped. The patient does not make up the omitted dose(s) at a later time.
- **Hold/Delay** = The current dose(s) of all drugs during a cycle is delayed. The patient does make up the delayed dose(s) when the patient meets the protocol criteria to restart drugs.
- **Discontinue** = The specified drug(s) are totally stopped.

Additional Adverse Events:

- The dose of ibrutinib will be omitted in case a patient experiences any of the following considered at least possibly related to ibrutinib:
  - Any Grade  $\geq 3$  or greater non-hematological toxicities (other than alopecia or fatigue) with the following considerations:
    - Grade 3 nausea, vomiting or diarrhea will be considered significant if they occur despite appropriate maximal anti-emetic and/or antidiarrheal therapy.
    - Grade 3 hyperglycemia will be a considered significant if the patient is symptomatic or glucose level is  $>300$  mg/ml despite appropriate administration of insulin and/or oral antidiabetic agents.
- Ibrutinib will be omitted until the non-hematologic AE recovers to Grade  $\leq 1$  or baseline and may be restarted at the original dose for the first occurrence.
- Upon each subsequent occurrence, ibrutinib is restarted at the next lower dose (as per Table 8.1) after recovery to Grade  $\leq 1$  or baseline.

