- If Grade  $\geq 3$  non-hematological AE or Grade 4 neutropenia and thrombocytopenia occurs at the lowest dose, discontinue ibrutinib treatment. The treatment with ibrutinib should also be discontinued entirely if ibrutinib is omitted for 4 consecutive weeks or at the discretion of the Principal Investigator for patient safety. Patients may then continue with ixazomib monotherapy.
- Patient will discontinue ibrutinib and enter survival follow-up if AE is grade  $> 3$  bleeding (other than bruising) that is probably or definitely attributed to ibrutinib.
- Patients who require a dose reduction during a given cycle will remain at that dose for at least 2 additional cycles. **At the investigator discretion, the dose of ibrutinib may be re-escalated after 2 cycles of a dose reduction in the absence of a recurrence of the toxicity that led to this reduction.**

This is particularly reasonable based upon the long-term safety data now available in Ibrutinib treated patients that show that most of the hematological or non-hematological AEs either decreased or remained stable.

If multiple AEs are seen, administer the dose based on the greatest reduction required by any single AE observed. Dose modifications are for AEs attributed to study treatment only. Dose modifications are not required for AEs if they are deemed unlikely or unrelated to study treatment.

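### Sections 8.0 and 8.3 give the Grade 3 hyperglycemia trigger in mg/ml, so its numeric limb cannot be met as printed; the unit should presumably be mg/dL

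*Combined protocol and SAP*

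**What the plan says.** Section 8.0 holds drug at the start of a cycle for non-hematologic toxicity of Grade 3 or higher that is at least possibly related to ixazomib and/or ibrutinib. It then qualifies Grade 3 hyperglycemia: "Grade 3 hyperglycemia will be considered significant if the patient is symptomatic or glucose level is >300 mg/ml despite appropriate administration of insulin". Treatment with oral antidiabetic drugs is named there as well.

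Section 8.3 sets a separate rule for ibrutinib: "The dose of ibrutinib will be omitted in case a patient experiences any of the following considered at least possibly related to ibrutinib". It carries the same qualification, and the unit is again mg/ml: "mg/ml despite appropriate administration of insulin and/or oral antidiabetic agents".

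Section 8.2, under its additional adverse events, has an ixazomib rule with no glucose condition. It covers Grade 3 or higher "non-hematological toxicity (other than peripheral neuropathy) considered at least probably related to ixazomib".

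Glucose is a scheduled test. The chemistry group in Section 4.1 includes "Uric acid BUN Glucose ALT/AST Alkaline phosphatase" and is drawn on Days 1, 8, 15 and 22 of cycle 1 and on Day 1 of cycles 2 to 24.

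**The concern.** The qualification has two limbs joined by *or*: symptoms, or a glucose value that stays above a threshold despite treatment. The second limb is there for the patient who feels well but whose glucose is not controlled. If the threshold is a value that cannot occur, that limb is void and the rule acts on symptoms alone.

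This is operative text, because it decides whether a dose is given. For the patient the second limb was written for, a literal reading requires no start-of-cycle hold and no omission of ibrutinib. The event would also not start the Section 8.3 sequence, in which the first occurrence restarts at the original dose and each later one at the next lower dose.

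**Working it through.** **Inputs**
- Threshold: 300 mg/ml (Sections 8.0 and 8.3).
- Conversion: 1 dL = 100 ml.
- Unit used elsewhere for serum measurements: mg/dL, for creatinine (Cockcroft-Gault equation, Section 3.15), immunoglobulin (Section 11.1) and the IgM rise that defines progression (Appendix III, footnote 2).

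**Step 1: convert the printed threshold.** 300 mg/ml × 100 ml/dL = 30,000 mg/dL, which is 300 g of glucose per litre. That this cannot occur in a living patient is general physiology, not a figure from the protocol.

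**Step 2: compare with the presumed intent.** 30,000 / 300 = 100. The printed threshold is 100 times the same number in mg/dL; equivalently, 300 mg/dL is 3 mg/ml.

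**Step 3: identify who is affected.** Take Grade 3 hyperglycemia that is at least possibly related to study drug.

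| Situation | As printed | With mg/dL |
|---|---|---|
| Symptomatic | Counts | Counts |
| Asymptomatic, 300 mg/dL or below on treatment | Does not count | Does not count (by design) |
| Asymptomatic, above 300 mg/dL despite treatment | Does not count | Counts |

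Only the last row changes. Grade 4 events fall under the general Grade 3-or-higher wording and are not affected.

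**Step 4: check whether another provision covers that row.**
- Section 8.2 omits ixazomib, but only if the event is at least *probably* related to it. Sections 8.0 and 8.3 act on *possible* relation, and Section 8.2 does not govern ibrutinib.
- Section 8.3 requires ibrutinib to be discontinued for a Grade 3 or higher non-hematological event at the lowest dose, with no glucose condition. This is mandatory but applies only at 140 mg, not at 420 mg or 280 mg.
- Section 8.3 also allows ibrutinib to be stopped "at the discretion of the Principal Investigator for patient safety", and Section 13.3 allows withdrawal on the investigator's opinion. Both are discretionary.
- Section 16.4 counts related Grade 3 or higher non-hematological events with no glucose threshold. It covers only cycle 1 of the 6-patient safety analysis and decides only the cohort dose of ixazomib.

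None of these supplies the missing threshold.

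**Step 5: count the scheduled occasions.** For the start-of-cycle rule, Day 1 of cycles 2 to 24 gives 24 − 1 = 23 readings after first exposure in a patient who completes treatment. Section 4.1, note 12 says: "After cycle 4, the patient may be allowed to come every other cycle". The minimum clinic visits after cycle 1 are then cycles 2, 3 and 4 (3 visits) plus the even cycles from 6 to 24 (10 visits), so 3 + 10 = 13. That is a lower bound, because under Section 7.3 "Clinical evaluation and blood tests can be obtained per test schedule and mailed/faxed to the consenting institution". The Section 8.3 rule is not tied to cycle starts, so Days 8, 15 and 22 of cycle 1 also apply to it: 23 + 3 = 26 readings. The numeric limb cannot be met at any of them. These are opportunities for the rule to act, not expected events.

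**The case against.** The strongest reply is that this is an obvious slip that would mislead nobody. The protocol uses mg/dL for other serum measurements, and a treating hematologist would read 300 mg/dL without hesitation. A similar slip appears in Section 1.1, where a hemoglobin cut-off is printed in g/L although Section 3.15 uses g/dL. On this view the failure exists only for a reader who applies an impossible number literally.

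The affected group is also narrow: asymptomatic, Grade 3, above threshold despite treatment, and at least possibly drug-related. Hyperglycemia is not among the toxicities listed for ixazomib (Section 15.17) or ibrutinib (Section 15.27), and the regimen in Section 7.1 has no corticosteroid. General oversight continues as well. Grade 3 and 4 events are reported regardless of attribution (Section 10.62), the investigators with the statistician and the DSMB each review the study at least twice a year (Section 16.51), the team may suspend accrual for unexpected adverse event profiles (Section 16.52), and patients with serious interfering conditions are excluded (Section 3.29g).

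Finally, the width of the affected band depends on the CTCAE glucose grades, which the protocol cites but does not reproduce.

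All of this stands as an argument about weight, and it keeps the point minor. It does not make the text right: reporting and periodic review do not direct a dose hold, and a site that reads mg/dL is applying a threshold the protocol does not state. The same unit is printed in two separate sections, so a text-extraction fault is unlikely.

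**Conclusion.** The concern holds. The glucose threshold is wrong as written in both dosing rules, by a factor of 100 if mg/dL was meant, and the numeric limb cannot operate. The consequence is limited to asymptomatic Grade 3 hyperglycemia above 300 mg/dL despite treatment.

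The conclusion rests on three assumptions:
- A glucose of 30,000 mg/dL cannot occur.
- The intended unit is mg/dL.
- At least part of the CTCAE Grade 3 range lies above 300 mg/dL. The affected group runs from a fraction of asymptomatic, treated Grade 3 events, if the range straddles 300, to all of them, if the range lies wholly above it.

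The documents give no rate for Grade 3 hyperglycemia, so the number of patients cannot be estimated; few are likely. No endpoint, sample size, decision rule or stopping rule uses the threshold. This is a unit correction worth making, not a material safety gap.

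**What to change.** Replace mg/ml with mg/dL in the hyperglycemia qualification in both Section 8.0 and Section 8.3, after the sponsor confirms that above 300 mg/dL is the intended threshold. The two sections should be changed together so that the hold rule and the omission rule stay aligned.

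The cost is one unit corrected in two places, with no change to the schedule of tests, the design or the analysis.
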